7 STUDY DESIGN

[figure not shown]
It is our hypothesis that a course of Ta1 administered to individuals at high risk for COVID-19 infection (hemodialysis patients 60 years and older) will reduce the rate of COVID-19 infection (primary objective) and severity of infection (secondary objective) with COVID-19, compared to untreated individuals in the same hemodialysis units with comparable risk. The secondary objectives also include an evaluation of the need for hospitalization in those patients who do not become infected with COVID-19.

Ideally, a randomized clinical trial with placebo control would be a preferred approach to address this hypothesis. However, the urgency of the current situation necessitates a simpler research design and implementation. Accordingly, we consider this a pilot study from which meaningful clinical data may rapidly be apparent.

After screening, renal dialysis patients 60 years and older who meet the inclusion criteria will receive Ta1 (1.6 mg) administered SC twice weekly for eight weeks. Individuals in the control arm will be followed on the identical protocol but will not receive twice weekly Ta1. After the treatment period, all subjects will be followed for efficacy outcomes for an additional 4 months. The total duration of the trial will be 1 year, including the estimated time required for screening.

A schema outlining the study design is presented in [Figure 1](#).

Figure 1: Study Design Schema

8 ENDPOINTS

8.1 Primary Endpoint

The primary efficacy endpoint is reduction in documented infection with COVID-19. This is defined as clinical suspicion (presence of symptoms of respiratory infection; see Appendix 1 for questionnaire) and laboratory confirmation of COVID-19 infection.

8.2 Secondary Efficacy Endpoints

The secondary efficacy endpoints are:

1. Need for hospitalization
 - This is defined by documentation in the case report form (CRF) of physician referral to hospital for admission
2. Hospital length of stay
 - The number of overnight stays in the hospital, entered into the CRF
3. ICU admission
 - Documentation in the CRF of physician recommendation for ICU transfer.
4. ICU length of stay
 - The number of overnight stays in the ICU
5. Mechanical ventilation
 - Documentation in the CRF of administration of mechanical respiratory assistance and length of time such assistance required
6. Duration of mechanical ventilation
 - Documented in the CRF by physician
7. Recovery time from COVID-19
 - Defined as testing negative, plus the time for full recovery as determined by physician
 - Documented in the CRF by physician
8. Change in any existing comorbidities (e.g., worsening congestive heart failure) or newly diagnosed disease
 - Documented in the CRF by physician
9. Incidence of secondary non-COVID-19 infections (relapses, superinfections and new infections).
 - Documented in the CRF by physician
10. Change in T lymphocyte subsets (CD4, CD8)
 - Samples taken at enrollment, at 8 weeks and at 6 months, or at time of hospital admission if that is required
11. Mortality
 - COVID-19 related, or non-COVID-19 related; documented in the CRF by physician.

8.3 Safety Endpoints

The safety endpoints include adverse events (AEs), vital signs and laboratory parameters.

9 STUDY POPULATION

9.1 Sample Size

A total of up to 240 patients will be enrolled. [name] (Co-Investigator) is a member of Nephrology Associates of Northern Virginia. This group manages over 700 hemodialysis patients at several sites in or near Fairfax Va. Three of these sites will participate in this research project. Members of the Nephrology Associates of Northern Virginia have reviewed the proposed research and have endorsed participation.

9.2 Inclusion Criteria

1. Age 60 years or greater
2. Signed informed consent
3. Patients with ESRD, receiving hemodialysis 2 or more times each week and expected to continue on dialysis indefinitely.

9.3 Exclusion Criteria

1. Patients on short-term hemodialysis, such as those with transient renal dysfunction associated with acute illness who are projected to have return in renal function
2. Patients for whom renal transplantation is anticipated within the next six months
3. Patients with an anticipated survival of less than 3 months
4. Patients with symptoms that might be attributable to COVID-19 infection (see Appendix 1 for symptom questionnaire)
5. Patients who test positive for SARS-CoV2
6. Patients with active infectious disease requiring antibiotics
7. Patients with hospitalization within the previous 3 months for acute myocardial infarction or congestive heart failure
8. Patients with advanced malignancy receiving cytotoxic chemotherapy
9. Patients with a Karnofsky Performance Scale score of less than 60
10. Patients with prior history of solid organ (kidney, liver, heart, lung, pancreas) or bone marrow transplant
11. Patients with active autoimmune disease on immunosuppressive medication
12. Patients receiving Plaquenil
13. Patients who have participated in an investigational drug or device trial in the previous 30 days
14. Patients with a history of allergy or intolerance to Ta1
15. Patients with any other medical or psychiatric condition that, in the opinion of the Investigator, would compromise patient safety or interfere with the objectives of the protocol or completion of the protocol treatment.

9.4 Removal of Subjects

In accordance with the Declaration of Helsinki, subjects have the right to withdraw from the study at any time for any reason. The Investigators (used throughout this protocol to refer to primary investigator or co-investigator) also have the right to withdraw subjects from the study. Subjects may be removed from the study for the following reasons:

Clinical Study Protocol: Ta1 to Prevent COVID-19 Infection in Elderly Renal Dialysis Patients

- Adverse events (AEs)
- At the request of the Investigator
- Subject is unwilling or unable to comply with study protocol (noncompliance)
- Termination of the study.

If the reason for removal of a subject from the study is an AE, the specific event and any related test results will be recorded on the CRF. The subject will be followed until the AE resolves, becomes chronic, or the subject is lost to follow up. If a subject dies, the date of the last dose of clinical trial material (CTM) and all observations collected up to the time of study termination will be recorded on the CRF as will be the reason for death.

If a subject or the Investigator chooses to discontinue CTM, the Investigator will inquire whether the subject will agree to participate in remaining study evaluations.

If a subject is removed from the study at the request of the Investigator, the date of the last dose of CTM and all observations collected up to the time of termination will be recorded on the CRF along with the reason for termination, and scheduled safety evaluations and follow-up examinations will be conducted, if possible.

The date that a subject discontinues and the reason for discontinuation will be recorded in the CRF. Subjects who discontinue after randomization will not be replaced. If a subject withdraws consent from the study during treatment, follow-up visit study procedures should be conducted, as possible.

10 STUDY TREATMENT

10.1 Treatment Plan

For those in the treatment arm, Ta1 at a dose of 1.6 mg will be administered SC in 1 mL of diluent upon completion of dialysis treatment twice weekly (separated by at least 2 full days without Ta1 injection) after dialysis for a total of 8 weeks. Control patients will not receive injection injections.

Subjects who report respiratory illness symptoms (see Appendix 1 for symptom questionnaire) at the designated inventory times (Table 1) or in the interval between those designated times will be tested for COVID-19 virus. If the COVID-19 assay is positive, this will complete the treatment phase of the research protocol for that individual. However, the subject will remain on study with continuation of the designated assessments to assess severity of disease (e.g., need for hospitalization, ICU management, mechanical ventilation, mortality).

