	
comparable risk. The secondary objectives also include an evaluation of the need for hospitalization in those patients who do not become infected with COVID-19.
 
Ideally, a randomized clinical trial with placebo control would be a preferred approach to address this hypothesis. However, the urgency of the current situation necessitates a simpler research design and implementation. Accordingly, we consider this a pilot study from which meaningful clinical data may rapidly be apparent.
 
After screening, renal dialysis patients 60 years and older who meet the inclusion criteria will receive Ta1 (1.6 mg) administered subcutaneously (SC) twice weekly for eight weeks. Individuals in the control arm will be followed on the identical protocol but will not receive twice weekly Ta1. After the treatment period, all subjects will be followed for efficacy outcomes for an additional 4 months.

Sample Size:	A total of up to 240 patients will be enrolled
Countries:	U.S.
Study Period:	Once FDA and IRB approval are obtained, the research team will promptly initiate the process of subject recruitment. Recruitment of all subjects will be completed in four months and the observation phase in one year.
Diagnosis and Main Criteria for Inclusion:	
 1. Age 60 or greater 2. Signed informed consent 3. End-stage renal disease (ESRD) who receive hemodialysis 2 or more times each week and are expected to continue on dialysis indefinitely.
Main Exclusion Criteria:	
 1. Patients on short-term hemodialysis, such as those with transient renal dysfunction associated with acute illness who are projected to have return in renal function 2. Patients for whom renal transplantation is anticipated within the next six months 3. Patients with an anticipated survival of less than 3 months 4. Patients with symptoms that might be attributable to COVID-19 infection (see Appendix 1 for symptom questionnaire) 5. Patients who test positive for SARS-CoV2

Clinical Study Protocol: Ta1 to Prevent COVID-19 Infection in Elderly Renal Dialysis Patients

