10.5 Method of Assigning Subjects to Treatment

Subjects who meet all inclusion and exclusion criteria will be centrally randomized 1:1 to receive either no treatment or 1.6 mg Ta1 in 1 mL doses to be delivered twice weekly after dialysis (with treatment days separated by at least 2 full days without Ta1 injection), via SC injection for 8 weeks, in accordance with a computer-generated randomization schedule prepared by the Inova Biostatistical core.

Randomization will be stratified by dialysis site.

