Subjects who report respiratory illness symptoms (see Appendix 1 for symptom questionnaire) at the designated inventory times (Table 1) or in the interval between those designated times will be tested for COVID-19 virus. If the COVID-19 assay is positive, this will complete the treatment phase of the research protocol for that individual. However, the subject will remain on study with continuation of the designated assessments to assess severity of disease (e.g., need for hospitalization, ICU management, mechanical ventilation, mortality).

In addition to infection with COVID-19, the following assessments will be collected and recorded at intervals in Table 1:

- Need for hospitalization
- Hospital length of stay
- ICU admission
- ICU length of stay
- Mechanical ventilation
- Mortality
- Incidence of secondary infections
- CD4, CD8, CD4/CD8.

Assessment for secondary infections will be documented in the CRF. Sites will be required to record all infections occurring from the time of enrollment until completion of the study 6 months after enrollment. Data will include the site of the infection, the evidence of infection, the organism cultured, and the antimicrobial susceptibility data.

The study will use the Inova Central Laboratory for conducting all laboratory investigations included in this study.

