Each sample size calculation depends on the type of endpoints, the variability of data, analysis methods used, and the minimal difference (or effect size) that we wish to be able to detect between the treatment (with Zadaxin) or control (without Zadaxin) groups. There are four types of endpoints for this study, dichotomous (e.g., infection of COVID19, the primary endpoint; ICU admission; or mortality), polytomous (e.g., health changes: no change, moderate, severe changes), counts (e.g., occurrence of non-COVID-19 infections), or continuous outcome variables (e.g., CD4, CD8, CD4/CD8, length of hospital stay, recovery time from COVID19). For a dichotomous outcome, a suitable model is a logistic regression with the treatment status (treated or not treated with Zadaxin) as the primary covariate, demographic information (age, gender, race), health/medical information (e.g., Karnofsky score, co-morbidity, and other biomarkers) and environmental information (treatment center, among others) as other relevant covariates. Assume the infection rate for the control group is about 0.40 and with a significance level of 0.05 (unless specified otherwise), if we use a simple logistic regression, a sample of size 200 will be able to detect a change at least at 0.185 in the infection rates between the treatment and control groups with a power of 80%. If we have a bigger sample size, say 234, we would be able to detect a change with a minimal difference of 0.17 with the same power or a minimum difference of 0.185 with a power of 86.5%. Using more comprehensive procedures (below) or if the actual difference is (much) larger than the minimal difference, we will have a (much) higher power than 80% to detect the actual difference. If we make a conservative adjustment for multiple comparisons incorporating other covariates after a pre-screening step, at an adjusted significance level 0.005, a sample of size 205 will provide 80% power for detecting a change of at least as large as 0.23. Using a multiple logistic regression model that takes into account the correlation among the various covariates, say if the correlation is 0.2, we can detect a minimal difference at 0.202 with a sample size of 200. If the correlation is 0.5, the minimum detectable difference would be 0.25. The highly correlated covariates that lead to multicollinearity will indicate the need for removal of redundant covariates in modeling the endpoint, and the removal will lead to more degrees of freedom in our study and the same power in detecting the even smaller difference. We will use all the sample we have and incorporate censored data or treat missing information with survival or a more comprehensive model than the logistic regression; thus, we expect to be able to detect a smaller minimal difference or have a much higher power to detect the actual difference in the infection rates than given above.

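### Follow-up after infection runs on the enrolment calendar and stops at month 6, so late infections have little time to show severity, and no retest interval is set for recovery time

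*Combined protocol and SAP*

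**What the plan says.** Section 10.1, repeated in 11.1, ends the treatment phase at a positive test and adds that "the subject will remain on study with continuation of the designated assessments to assess severity of disease". Section 11.1 has the severity items recorded at the Table 1 times. Table 1 counts from enrolment: weekly to week 8, then months 3 to 6. The same section has infections recorded "until completion of the study 6 months after enrollment".

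Nothing else in the protocol extends follow-up for an infection still open at month 6:

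- Collection of adverse events and serious adverse events also ends at the 6-month visit (13.5, 13.7).
- Following an adverse event to resolution (9.4) applies to subjects removed from the study because of it.
- The only assessment triggered by an event after infection is the CD4/CD8 sample at hospital admission (8.2, item 10).

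Secondary objective 1 (6.2) compares the course of disease in subjects who become infected: hospitalisation, ICU stay, ventilation and survival. Section 15.2 names logistic regression for binary outcomes and general linear regression for continuous ones.

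Recovery time (8.2, item 7) is "Defined as testing negative, plus the time for full recovery as determined by physician". No retest interval after a positive result is stated. Table 1 schedules the SARS-CoV2 assay at weeks 2, 4, 6 and 8 and months 3 to 6, but sections 12.4 and 12.7 do not list it.

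On the calendar, the synopsis says "Recruitment of all subjects will be completed in four months and the observation phase in one year".

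**The concern.** A severity comparison among infected subjects is fair only if each has comparable time in which to be admitted, ventilated or die. Here that time depends on when the infection falls. A subject infected in week 3 has about five months. A subject with symptoms and a positive test at the month 6 visit has almost none, and would enter a logistic model as not hospitalised and alive. Nothing in 15.2 adjusts for time since infection. The single mention of censored data is a general intention in 15.1, made about infection rates.

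Two things are at stake. Severe outcomes are under-counted in both arms. And if Ta1 delays infections, more of its infections sit where severity is cut off, so the error leans towards Ta1. Recovery time has a separate problem: without a retest rule, the date of the negative test may simply be the date of the next scheduled visit.

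**Working it through.** **Inputs.** Control risk 0.40 and difference 0.185, hence 0.215 with Ta1 (15.1); 200 completers (15.1), subjects who "will be centrally randomized 1:1" (10.5), so 100 per arm; follow-up of 8 weeks plus 4 months, about 182 days (section 7). Table 1 assays are taken as days 14, 28, 42, 56, 91, 122, 152 and 182. The documents give neither the timing of infections nor the delay from infection to a severe event. Both are assumptions below.

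**1. The plan's own figure.** Section 15.1 states that "a sample of size 200 will be able to detect a change at least at 0.185 in the infection rates" with 80% power. Sidedness is not stated; two-sided 0.05 is assumed. By the log-odds-ratio formula, n per arm = (1.960 + 0.842)² × [1/(0.40 × 0.60) + 1/(0.215 × 0.785)] / (logit 0.40 − logit 0.215)² = 7.849 × (4.167 + 5.925) / 0.7914 = 100.1, so N is about 200. The simple two-proportion formula gives 81.4% power at 100 per arm. The figure is reproduced. Expected infections: 40 + 21.5 = 61.5.

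**2. Infections with under 28 days of follow-up.** With constant hazard and six-month risk p, the share in the last w days is [(1 − p)^((182 − w)/182) − (1 − p)]/p.

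- Control, w = 28: (0.6491 − 0.6)/0.4 = 12.3%, or 4.9 of 40.
- Ta1, w = 28: (0.8148 − 0.785)/0.215 = 13.9%, or 3.0 of 21.5.
- Together 7.9 of 61.5 (12.8%). For w = 14, 3.9 of 61.5 (6.3%).

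Other timing, w = 28:

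- Uniform: 28/182 = 15.4%, or 9.5.
- Density falling linearly to zero at month 6: (28/182)² = 2.4%, or 1.5.
- Density rising linearly from zero: 1 − (154/182)² = 28.4%, or 17.5.

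**3. Severe events missed.** Simulation with an assumed lognormal delay from infection to event (log-SD 0.5 or 0.7) and infections spread evenly in time. With a median delay of 10 to 20 days, 29% to 60% of events are captured for infections in the last 28 days, against 96% to 99.9% for infections before day 152. With a 5-day median, 77% to 80% are captured for the last 28 days.

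**4. Imbalance between arms.** Share of infections in the last 28 days, constant background hazard:

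| Arm and assumption | Share |
|---|---|
| Control | 12.3% |
| Ta1, proportional effect reaching 0.215 | 13.9% |
| Ta1, hazard halved in the 8 treatment weeks only | 15.1% |
| Ta1, full protection in the 8 treatment weeks only | 19.3% |

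Let m be the fraction of severe events missed for those infections (0.40 to 0.71 from step 3), and let earlier infections be fully captured. The Ta1/control severity ratio is then multiplied by (1 − m × Ta1 share)/(1 − m × control share). For the proportional effect this is 0.993 (m = 0.40) to 0.988 (m = 0.71). For full on-treatment protection it is 0.971 to 0.946. The shift is about 1% to 5%.

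**5. Recovery read only from Table 1 assays.** Take a true 14 days to a negative result.

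- Infected in the first 28 days: mean wait to the next test 14/2 = 7 days, read as 21.
- Infected on days 56 to 120, so negative on days 70 to 134: mean wait (21 × 10.5 + 31 × 15.5 + 12 × 24)/64 = 15.5 days, read as about 29.
- Infected on days 152 to 182: a negative is seen only if infection is by day 168, so 14/30 = 47% are never seen negative. Those seen average 14 + 8 = 22 days. For a true 21 or 28 days, 70% and 93% are never seen negative.

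**6. Calendar.** Recruitment 4 + follow-up 6 = 10 months. A 28-day window from an infection at month 6 adds 28/30.4 = 0.9, giving 10.9 months. The 14 days allowed for screening (Table 1, note 1) bring it to about 11.4 of the 12.

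**The case against.** The strongest reply is that the effect is small and confined. Section 8.2 does not restrict hospitalisation, ICU admission, ventilation or mortality to infected subjects. Compared across all randomised subjects, both arms have the same six months. The trial is a declared pilot, and these are secondary endpoints. All of this stands. So does the point that an infected-only comparison already conditions on an event after randomisation, which no follow-up window cures. But 6.2 makes that comparison the first secondary objective, and there the unequal observation time remains.

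On bias towards Ta1, the on-treatment-only scenarios do not match the planned effect: even full protection for eight weeks gives a six-month risk of 0.298, not 0.215. With a proportional effect the shares are nearly equal (12.3% and 13.9%). This stands too. A reader might infer a material tilt towards Ta1; the figures do not support that.

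A reader might also infer that recovery can be known only to within two or four weeks. The documents do not go that far. Full recovery is the physician's judgement, unscheduled retests are not excluded, section 11.1 has a nurse take symptoms twice weekly, and subjects attend dialysis at least twice weekly. What is established is that no retest interval is defined and that Table 1 disagrees with 12.4 and 12.7. Hospital and ICU stays are counted in nights, so visit spacing does not coarsen them.

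Finally, not every positive swab at month 6 counts as an infection: section 8.1 also requires symptoms.

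**Conclusion.** The point holds as a limited weakness in the secondary endpoints. Infections near month 6 enter the severity comparison of secondary objective 1 with little or no observation, and the named models do not allow for it. At the planned rates and an assumed constant hazard, this affects about 8 of 61.5 infections. The range of 1.5 to 17.5 reflects how little is known about timing. The cut-off makes late infections look milder; the resulting tilt towards Ta1 is modest and arises only if Ta1 shifts infections later.

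It is tempting to say that sparse retesting also makes later infections look milder. It does the reverse: if only the Table 1 assays are used, recovery is rounded up to the next test and later recovery looks longer. Only the month 6 cut-off shortens what is seen, by leaving some recoveries unobserved. The primary endpoint is not affected, since its six-month window is the same in both arms.

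**What to change.** In 10.1, 11.1 and Table 1, collect hospitalisation, ICU admission, ventilation and vital status for a fixed 28 days after the first positive test, even where this passes month 6. Compare infected subjects within that window.

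For recovery, record the actual dates of symptom resolution and of the first negative test at dialysis attendances. The Appendix 1 inventory will not serve as the source, because it is monthly after week 8. State the retest interval and reconcile Table 1 with 12.4 and 12.7. Analyse recovery as time from the first positive test, censoring subjects not recovered by the end of follow-up, and state how deaths before recovery are handled.

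The cost is protocol wording and up to four more weeks of record collection for roughly 12% to 14% of infected subjects (constant-hazard figure), in patients already attending dialysis. The stated year is long enough. The downside is that events beyond 28 days have to be described separately.
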